To date, information regarding the health effects of exposures to drinking water contaminated with TCE and PCE are extremely limited. The findings of this study at Camp Lejeune should further our understanding of the health effects of TCE or PCE exposure from community drinking water and will help us better focus our prevention efforts.

Study Design/Locations

ATSDR will conduct a case-control study of cases of childhood cancer or specific birth defects and a random sample of controls to assess the relationship between VOC exposure and the incidence of childhood cancer and birth defects in children born to parents while residing at Camp Lejeune from 1968 to 1985. Both cases and controls may currently reside anywhere in the United States.

Objectives

The overall objective of this study is to examine the associations between maternal exposures within a 1-year period before child's birth to TCE and PCE in drinking water at Camp Lejeune during the period of 1968-1985 and risk of specific birth defects and childhood leukemia (ALL) in offspring.

Hypotheses

1. a. There is no association between ever drinking TCE/PCE contaminated water during the first trimester and the risk of specific birth defects.

- b. There is no association between ever drinking TCE/PCE contaminated water during each trimester and the risk of leukemia (ALL).
- 2. a. There is no association between exposures to different concentrations of TCE/PCE in drinking water during the first trimester and the risk of developing specific birth defects.
 - b. There is no association between exposures to different concentrations of TCE/PCE in drinking water during each trimester and the risk of leukemia (ALL).
- 3. a. There is no association between exposures during the first trimester to ever/never or to different concentrations of TCE/PCE in drinking water, taking into account the amount of water used (i.e., showering, hand washing dishes) or consumed by the mother, and the risk of specific birth defects.
 - b. There is no association between exposures during each trimester to ever/never or to different concentrations of TCE/PCE in drinking water, taking into account the amount of water used (i.e., showering, hand washing dishes) or consumed by the mother, and the risk of leukemia (ALL).

METHODS

Study Rationale

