 - (b) hydraulic and water-quality calibration and testing of the present-day model based on the field data;
- II. Development of historic distribution system models through the study period, 1968–1985;
 - (a) historical reconstruction of hydraulics within the water-distribution system;
 - (b) historical reconstruction of fate and transport of contaminants within the water-distribution system;
 - (c) comparison of historical contaminant concentrations with measured tap sample data for specified locations and times; and
 - (d) assignment of the monthly contaminant concentrations for historical period for all study locations.

The exposure assessment methods in the current study will most likely estimate concentrations by year and housing complex. However, depending on the completed model, it may be necessary and possible to estimate contaminant levels at different locations within each housing complex.

Study Population

The 1998 ATSDR adverse pregnancy outcomes study at Camp Lejeune obtained birth certificate information on the 12,493 children born to parents known to have been stationed at Camp Lejeune during pregnancy between 1968 and 1985. These years were chosen because 1968 is the first year that birth

certificates were computerized in North Carolina and 1985 is the last year that VOC contamination was detected at the base. This time period also provided a sufficient sample size to conduct the study. An estimated additional 4,000 births occurred elsewhere to personnel who were stationed at Camp Lejeune at some point during pregnancy during the 1968-1985 timeframe (ATSDR 2003). A referral process was used to obtain information on personnel who were pregnant while residing at Camp Lejeune during 1968-1985 but who delivered elsewhere. Additionally, a media campaign was used to find personnel stationed at Camp Lejeune during pregnancy who could not be located as well as the estimated 4,000 births that occurred elsewhere. Names of personnel identified through referral or by the media campaign were cross-referenced with military databases.

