While there is no direct public health benefit to those children potentially harmed by the

contaminated drinking water at Camp Lejeune, the information gained during the study will help advance research on this topic and may help future children. Only a small number of studies have looked at the risk of birth defects and childhood cancers among children born to mothers exposed during pregnancy to volatile organic compounds (VOCs) in drinking water.

This study is unique in that it will examine the associations between well-defined exposures to TCE/PCE in drinking water and risk of developing specific birth defects and childhood leukemia. The associations between exposure to TCE/PCE during various time periods of interest (pre-conception/trimesters/entire pregnancy) and the risk of particular health outcomes can be thoroughly examined.

REFERENCES

- Agency for Toxic Substances and Disease Registry. 1997. Toxicological profile for Tetrachloroethylene (Update). Atlanta: US Department of Health and Human Services.
- Agency for Toxic Substances and Disease Registry. 1997. Toxicological Profile for Trichloroethylene. (Update). Atlanta: US Department of Health and Human Services.
- Agency for Toxic Substances and Disease Registry. 1990. ATSDR Preliminary Public Health Assessment for ABC One-Hour Cleaners. Atlanta: US Department of Health and Human Services.
- Agency for Toxic Substances and Disease Registry. 1997. Public Health Assessment: U.S. Marine Corps Camp Lejeune, Onslow County, North Carolina. Atlanta: US Department of Health and Human Services.
- Agency for Toxic Substances and Disease Registry. 1998. Volatile Organic Compounds in Drinking Water and Adverse Pregnancy Outcomes: U.S. Marine Corps Camp Lejeune. Onslow County, North Carolina. Atlanta: US Department of Health and Human Services.
- Agency for Toxic Substances and Disease Registry. 2000. Analysis of the 1998 Water-Distribution System Serving the Dover Township Area, New Jersey. Atlanta: US Department of Health and Human Services.

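### Exposure Assessment gives two time resolutions, monthly and most likely yearly, for one exposure model; yearly values would blur the trimester exposures on which every hypothesis rests

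*Protocol*

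**What the plan says.** Protocol, Methods, Exposure Assessment sets out the historical reconstruction in numbered steps. Step II(d) is the "assignment of the monthly contaminant concentrations for historical period for all study locations". The sentence directly after the list says: "The exposure assessment methods in the current study will most likely estimate concentrations by year and housing complex". The qualification that follows is that "it may be necessary and possible to estimate contaminant levels at different locations within each housing complex". It concerns place and leaves the time unit as it was.

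The Hypotheses section needs exposure within parts of a pregnancy:

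- 1a concerns "ever drinking TCE/PCE contaminated water during the first trimester".
- 2a concerns "exposures to different concentrations of TCE/PCE in drinking water during the first trimester".
- 2b concerns "exposures to different concentrations of TCE/PCE in drinking water during each trimester".
- 1b uses each trimester for ever/never exposure.
- 3a and 3b repeat these windows with water use taken into account.

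Data Analysis likewise defines exposure over particular periods within the year before birth. The Discussion says that associations for pre-conception, trimester and whole-pregnancy windows "can be thoroughly examined".

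**The concern.** The time unit of the central exposure variable is stated twice, in adjacent lines, with different answers. This is not a detail left for later. A monthly series can be cut into trimesters; a yearly one mostly cannot, because each annual figure mixes months inside the window with months outside it.

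The protocol's own background shows that levels changed within years. Wells were rotated, and contaminant levels followed the wells in service. Contaminated wells were closed in January and February 1985. Holcomb Boulevard housing received Hadnot Point water for 12 days from January 27, 1985. The same housing left the Hadnot Point supply at some point in 1972.

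Two things are at stake. First-trimester exposure for the birth-defect hypotheses could be misclassified. The three trimester results for leukemia, from 12 to 15 cases, could resemble each other because of how exposure was assigned and yet be read as distinct findings. If the unit stays open, it will be chosen after the model output is seen.

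**Working it through.** The protocol gives no figure on this point to reproduce. The check compares the texts and then sizes the consequence under stated assumptions.

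**1. Texts side by side.** Step II(d): monthly, all study locations. Next sentence: yearly, by housing complex, hedged as likely. Exception: finer location only. Hypotheses 1a, 2a, 3a: first trimester. Hypotheses 1b, 2b, 3b: each trimester. The first two statements cannot both describe the assigned concentration.

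**2. Pregnancies inside one calendar year.** Assumptions: yearly means calendar year, conceptions are uniform over the year, and the mother does not move. With gestation of L months, the share is (12 − L)/12:

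- L = 9: 3/12 = 25%
- L = 8: 4/12 = 33%
- L = 7: 5/12 = 42%

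These pregnancies get the same annual value in every trimester. At L = 9 the other 75% cross a year boundary, and their trimesters differ only through two annual means.

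**3. How much is blurred.** No monthly series is given, so a range was simulated: 240,000 months of a first-order autoregressive series, three-month trimesters and a nine-month pregnancy. Trimester means from the monthly values were compared with trimester means from calendar-year averages. The month-to-month correlation is an assumption.

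| Month-to-month correlation | True vs annual-based first trimester | First vs third trimester, true | First vs third trimester, annual-based |
|---|---|---|---|
| 0 | 0.48 | 0.00 | 0.54 |
| 0.5 | 0.60 | 0.04 | 0.58 |
| 0.8 | 0.78 | 0.33 | 0.66 |
| 0.9 | 0.87 | 0.58 | 0.76 |
| 0.95 | 0.94 | 0.77 | 0.86 |

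Annual values track first-trimester exposure poorly when levels jump and well when they drift. In every row they make the first and third trimesters look more alike than they are.

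**4. Documented within-year changes.** The 12-day hookup is 12/365 = 3.3% of a year but 12/91 = 13% of a trimester. A nonzero annual Holcomb value for 1985 would mark trimesters later that year as exposed. Take exposure in the contaminated systems to end in February 1985, with a 9-month gestation. Births from June 1985 then have the third trimester wholly after closure, births from September also the second, and births in December all three. A nonzero 1985 mean labels those windows exposed. For 1972, the date of the Holcomb switch is not given; unless it fell at a year boundary, an annual value mixes two sources.

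**The case against.** The yearly sentence is hedged, was written before modelling, and sits in a section that admits historical measurements are scarce. The plan also uses categorical exposure because of uncertainty, promises extensive sensitivity analyses of the water model, and does not interpret results on significance alone. All of this is fair. It softens the consequence but does not say which unit applies.

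A reader might infer that yearly values make the trimester hypotheses untestable. The documents do not support that. Date of birth is available, residence is collected for a year either side of birth, and housing records fix the address. Trimester exposure can be built from annual values weighted by residence dates. It will differ where a mother moves or a pregnancy crosses a year boundary. Ever/never status depends largely on which system served the home, although 1972 and 1985 show that a mother who never moved could change status within a year.

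Nor does it follow that the three leukemia results would be near copies of each other. With time-weighted values and no move, the second and third trimesters are identical only when both fall in one year, (12 − 6)/12 = 50%, and the first and third in 25%.

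A reader might also expect odds ratios to be diluted. No bias was computed. Replacing a short-window value by a longer average is largely Berkson-type error, which mainly costs precision, whereas marking unexposed windows as exposed is a different error. The net direction is open.

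The 1985 example is small. December 1985 births are 1 month of 18 × 12 = 216, about 0.5%. If any pregnancy on base in 1985 counts, conceptions from March to December are 10/216, about 5%. Nothing in the protocol says that an annual mean would be applied across a known closure date.

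**Conclusion.** The contradiction stands: two time units are stated for one exposure model, and every hypothesis depends on which is used. Following the yearly sentence would blur trimester exposure, not preclude its study. The size runs from mild to severe, with a correlation between true and annual-based first-trimester level from 0.94 down to 0.48, depending on how fast levels changed, which the protocol does not establish. The 25% with identical trimester values rests on a 9-month gestation, uniform conceptions, no move and a calendar-year reading. Mislabelling around the 1985 closure and the hookup is possible but affects few births. Neither untestable hypotheses nor a known direction of bias can be concluded. With only annual values, the Discussion's statement about trimester windows would promise more than the data could give.

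**What to change.** In Exposure Assessment, delete the yearly wording and state month by housing complex, or finer location, as the unit of exposure assignment, consistent with step II(d).

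Add a fallback, fixed before the model is complete. If it supports only annual values:

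1. First-trimester exposure for birth defects is still built from first-trimester residence dates and labelled as based on annual means. Known within-year changes, such as the well closures and the Holcomb hookup, are applied by date. A whole-pregnancy mean should not replace it, because hypotheses 1a to 3a concern the first trimester.
2. Trimester-specific leukemia results (1b, 2b, 3b) are not interpreted as separate pieces of evidence.
3. The Discussion's statement that trimester associations "can be thoroughly examined" is qualified accordingly.

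The cost is protocol wording. Monthly reconstruction is already a listed step, and the water modelling is not yet finished.

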The Agency for Toxic Substances and Disease Registry (ATSDR) is required by law to conduct a public health assessment at each of the sites on the National Priority List (NPL). The aim of each assessment is to determine whether the population residing around a particular site might have been exposed to any toxic substance and also to assess whether there might have been any adverse health effects resulting from this exposure. Known health effects are documented in these assessments and public health recommendations are made accordingly. Potential health effects are also identified and referred to ATSDR scientists for additional investigation.

As part of this health assessment process, mixtures of volatile organic compounds (VOCs) containing high levels of trichloroethylene (TCE) and tetrachloroethylene (PCE) were documented in two drinking water supplies at Camp Lejeune over a period of 34 months. The population that was supplied with this water was slightly more than half of all residents in family base housing. Because this population consisted of a large proportion of young married women, concern was raised about potential health effects on fetuses exposed to toxic substances in utero.

U.S. Marine Corps (USMC) Base Camp Lejeune covers an area of approximately 233 square miles in the City of Jacksonville, North Carolina. Base housing for enlisted personnel, officers, and their families were located in 15 different areas on the base. Based on Camp Lejeune family housing records, we estimate that at least 180,000 people were potentially exposed to VOCs while living in family housing during 1968-1985. This estimate is derived from information that almost 90,000 military members were assigned to family housing during this time period (ATSDR 1998), and family housing was assigned to military members with two or more people in their household. To meet the water needs of a base this size, an average of 8.3 million gallons of water was distributed daily. To do this, more than 100 wells had been drilled. Almost all of these wells used a sand aquifer which is permeable to contamination (Weston, Inc 1992).

In 1982, groundwater contamination was detected in wells that fed the family base-housing areas on

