Potential controls consist of children without these birth defects or childhood leukemias who were born to mothers who resided at Camp Lejeune during their pregnancies in the same time period and participated in the survey. We will attempt to enroll ten times as many controls as cases. One control group will be utilized for all of the cases of both birth defects and childhood leukemias. Control selection will be performed by using a randomization procedure. The only risk factor that has a skewed distribution is maternal age. At ages 30-34 and >34, the percentages of mothers who delivered at Camp Lejeune were approximately 7.5% and 2%, respectively (ATSDR 1998). Although maternal age has a skewed distribution in the study population, we could not match on this risk factor because we lacked information on maternal age for about 20% of the study population.

The order of preference for participants in the study is 1) the biological mother of the case or control child, 2) the biological father of the case or control child, or 3) the case or control child. If the biologic father is not the initial study respondent, we will also attempt to contact him to obtain more detailed information about his medical history, lifestyle habits, and occupational history.

Sample Size, Power, and Precision of Risk Estimates

For a sample size calculation, the values of the alpha error, beta error, and minimum meaningful effect size are selected, and the required sample size is calculated. However, since the number of exposed subjects and the total number of cases for each outcome cannot be increased, and the alpha and beta errors should be set as low as possible, the only parameter that can vary is the meaningful effect size. If the a.) alpha error

is set at 0.10 (i.e., 90% confidence interval) b.) beta error is set at 0.20 (i.e., 80% power) and c.) the expected exposure prevalence is 40%, the following ORs can be detected given the number of cases for each outcome:

- an OR of 4.3 or greater can be detected for 15 cases with NTDs and 450 controls and an OR of 2.85 or greater can be detected for 28 cases with NTDs and 448 controls,
- an OR of 3.5 or greater can be detected for 20 cases with oral cleft defects and 440 controls and an OR of 2.5 or greater can be detected for 36 cases with oral cleft defects and 432 controls, and

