- an OR of 5.15 or greater can be detected for 12 cases with leukemia and 444 controls and an OR of 4.3 or greater can be detected for 15 cases with leukemia and 450 controls.

An exposure prevalence of 40% is from the previous study of SGA at Camp Lejeune (ATSDR 1998; Sonnenfeld et al. 2001). It represents the percent of births born at Camp Lejeune that were estimated to ever have been exposed to PCE during the study period. Although we will not know for sure until after the water modeling is completed, it is expected that about half of the births were exposed to PCE. It is also expected that the levels of exposure to PCE varied over the study period such that there will be a significant range of exposures to PCE. The situation for TCE is less clear, and probably a large majority of the births were not exposed to TCE. Again, the TCE levels will vary over the study period so there will be a range of exposures.

All 79 children with the following confirmed or pending birth defects and childhood cancers who were born to parents residing at Camp Lejeune during their pregnancy between 1968 and 1985 will be recruited for the study: 28 NTDs, 36 oral cleft defects, and 15 leukemias. We expect a 90% participation rate because all of the participants took part in the Camp Lejeune Survey in 1999-2002 and gave permission to be contacted for future studies. Additionally, many survey participants have telephoned ATSDR to request the results of the survey and inquire about future studies. A 90% participation rate will yield 71 cases: 25 NTDs, 32 oral cleft defects, and 14 leukemias. Using one control group, we will attempt to enroll ten times as many controls as cases which will yield a comparison group of 710 children to allow

enough controls for the analyses.

Enrollment of Study Participants

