All electronically entered information obtained from questionnaires will be reviewed for missing data and ambiguous responses. Individual interviewers will be contacted to complete missing data where possible or to call back participants to fill in the missing information. Internal consistency and validity programs will be used to identify and correct coding and data entry errors. Data entry will be verified for accuracy by using software data match features.

Reimbursement

No remuneration will be offered to participants. In addition, no invasive procedures will be performed which could potentially cause injury or the need for medical treatment.

Data Analysis

The exposure variables include exposure status, concentration level, and/or percent of water from a contaminated source during specific time periods of interest in the one-year period before the child's birth. TCE and PCE will be evaluated separately. The exposure metrics will be ever/never, a categorization of the contaminant levels, and a categorical exposure variable that incorporates water usage and consumption as well as contaminant levels. Categorical exposure variables will be used because of the uncertainties involved in estimating exposures. We will look at the distribution of contaminant levels to determine appropriate cutoff values for the categorical variables. Those exposed to TCE or PCE will be compared to those without exposure to either chemical in the drinking water. Extensive sensitivity analyses will be conducted on the water modeling.

Descriptive statistics will be presented for the potential risk factors. Verified cases of birth defects and childhood cancers will be compared with controls using unconditional logistic regression. It may be necessary to use exact or conditional logistic regression methods if the data are too sparse. We will consider doing a secondary analysis including unconfirmed cases because the true odds ratio lies between the results obtained by analyzing only confirmed cases and confirmed and unconfirmed cases because unconfirmed cases are not all negative (do not have the condition) or all positive (do have the condition).

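### Detectable odds ratios are given only at 40% exposure, although the same section expects about half of births to be PCE-exposed; by the method that reproduces them, power at 50% is 69-76%, not 80%

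*Protocol*

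**What the plan says.** In the protocol, Sample Size, Power, and Precision of Risk Estimates, case numbers and the number exposed are treated as fixed. The detectable OR is therefore the only output. Alpha is 0.10, tied to a 90% confidence interval, and power is 80%. The section then states that "the expected exposure prevalence is 40%, the following ORs can be detected" and lists six rows:

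- neural tube defects (NTDs): 4.3 (15 cases, 450 controls) and 2.85 (28, 448)
- oral clefts: 3.5 (20, 440) and 2.5 (36, 432)
- leukemia: 5.15 (12, 444) and 4.3 (15, 450)

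The following paragraph gives the source: "An exposure prevalence of 40% is from the previous study of SGA at Camp Lejeune", where it is the share of births ever exposed to PCE. The same paragraph says that certainty must wait for the water modeling, but "it is expected that about half of the births were exposed to PCE". For TCE it says that "probably a large majority of the births were not exposed to TCE".

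Under Data Analysis, the two chemicals are evaluated separately, and "Those exposed to TCE or PCE will be compared to those without exposure to either chemical in the drinking water".

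**The concern.** The section holds two expected prevalences for the same chemical, 40% and about half, and calculates only from the first. A reader would probably take 40% as the cautious choice, since exposure nearer one half usually helps a case-control comparison. At ORs of 2.5 to 5 with 12 to 36 cases the reverse holds between 40% and 50%: the exposed share among cases is already high, so the gap between cases and controls narrows as control exposure rises. The listed ORs are then too favourable at the protocol's own expectation for PCE. What is at stake is the accuracy of the only quantitative statement of what the study can detect, chiefly for leukemia and for the NTDs confirmed so far.

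**Working it through.** **Inputs.** Case counts, control counts, ORs, alpha 0.10 and the 40% are from the sample-size section; alpha is read as two-sided because it is tied to a 90% interval. The 50% stands for that section's expectation of about half.

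**Formulae.** With control exposure p0, exposure among cases is p1 = OR x p0 / (1 + p0 x (OR - 1)). With a cases and c controls, the pooled proportion is pb = (a x p1 + c x p0)/(a + c). Then:

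- s0 = sqrt[pb(1 - pb)(1/a + 1/c)]
- s1 = sqrt[p1(1 - p1)/a + p0(1 - p0)/c]
- d = p1 - p0 - (1/a + 1/c)/2, the last term being the continuity correction
- power = Phi[(d - 1.645 x s0)/s1]

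**Worked row: 12 leukemias, 444 controls, OR 5.15.**

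- At 40%: p1 = 2.06/2.66 = 0.774, pb = 0.410, s0 = 0.144, s1 = 0.123, d = 0.374 - 0.043 = 0.332. Power = Phi[(0.332 - 0.237)/0.123] = 78%.
- At 50%: p1 = 2.575/3.075 = 0.837, pb = 0.509, s0 = 0.146, s1 = 0.109, d = 0.337 - 0.043 = 0.295. Power = Phi[(0.295 - 0.241)/0.109] = 69%.

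**All rows.** The 40% columns reproduce the plan; the 50% columns change only the prevalence.

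| Cases / controls | Stated OR | Power at 40% | Power at 50% | OR for 80% power at 40% | OR for 80% power at 50% |
|---|---|---|---|---|---|
| 12 / 444 (leukemia) | 5.15 | 78.0% | 69.0% | 5.37 | 6.57 |
| 15 / 450 (NTD or leukemia) | 4.3 | 79.4% | 72.2% | 4.35 | 5.01 |
| 20 / 440 (cleft) | 3.5 | 80.1% | 74.6% | 3.50 | 3.83 |
| 28 / 448 (NTD) | 2.85 | 80.1% | 76.1% | 2.85 | 3.01 |
| 36 / 432 (cleft) | 2.5 | 79.5% | 76.3% | 2.52 | 2.62 |

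The stated ORs are matched closely at 40%; the 12-case row is the loosest match. Without the correction, power at 40% would be 84-87%, so the uncorrected test is not the one behind the listed figures.

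**Dependence on the test.** Power at 50%, same counts and ORs, by exact enumeration of the 2x2 tables:

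- score and likelihood-ratio tests: about 82-84% in every row
- Wald: 81-82% for 20, 28 and 36 cases; 76% for 15; 66% for 12 (tables with an empty case cell counted as misses)
- Fisher, upper tail 0.05: 71-77%

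**Counts from one scenario.** The section expects 90% participation among 79 cases (28 + 36 + 15), giving 71 (25, 32 and 14), with ten controls per case, 710. Detectable ORs by the corrected formula:

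| Cases / controls | At 40% | At 50% |
|---|---|---|
| 25 NTDs / 710 | 3.0 | 3.2 |
| 32 clefts / 710 | 2.6 | 2.7 |
| 14 leukemias / 710 | 4.6 | 5.3 |

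**The case against.** **The calculation is conditional and correct.** The ORs are stated for a 40% prevalence and reproduce at 40%. The source of that figure and the uncertainty before water modeling are both disclosed. This stands: there is no arithmetic error. What remains is that the condition is labelled as the expected prevalence, while the protocol's own expectation for PCE is higher and has no OR attached.

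**The shortfall depends on the test.** The planned primary analysis is unconditional logistic regression with 90% intervals, which has no continuity correction. This also stands. A reader might infer that the primary analysis will have only 69-76% power; the document does not support that. For likelihood-ratio or score inference, power at 50% stays above 80%. The shortfall appears with the corrected method used for sizing, with the exact methods the protocol foresees for sparse data, or with Wald inference in the 12- and 15-case rows.

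**The hypotheses concern trimesters.** Birth defects are tied to the first trimester and leukemia to each trimester. Prevalence in one trimester cannot exceed prevalence over the pregnancy, and the protocol does not say how far below it lies. At 30%, the corrected formula gives 79-82%. So the point applies to PCE ever/never, the contrast from which the 40% was taken, and not automatically to the trimester contrasts.

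**The TCE-only share is unknown.** A reader might try to derive it by subtracting 40% from the statement in the Introduction that "The population that was supplied with this water was slightly more than half of all residents in family base housing". That does not work: one figure counts residents and accompanies a 34-month period of documented contamination, the other counts births over 1968-1985. Only the direction can be stated. Removing births exposed to TCE alone shrinks the reference group and drops cases and controls; starting from 40% or 50% PCE exposure, and assuming no excess risk in those births, this lowers power further.

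**No decision rests on these ORs.** A reader might fear that a null result would be taken to exclude them. The protocol points the other way: Data Analysis does not rest interpretation solely on significance, and the Discussion admits limited power and wide intervals.

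**Conclusion.** The point holds in limited form. The sample-size section is internally inconsistent on expected PCE prevalence and reports detectable ORs only at the more favourable figure. By the method that reproduces those ORs, power falls from 78-80% at 40% to 69-76% at 50%. The OR needed for 80% power rises from 5.15 to about 6.6 (12 cases) and from 4.3 to about 5.0 (15 cases). The other rows move little: 3.5 to 3.8, 2.85 to 3.0 and 2.5 to 2.6.

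This rests on reading about half as 50%, on two-sided alpha 0.10, on the continuity-corrected test, on ever-exposure to PCE, and on no births being removed as TCE-only. It is a fault in the stated precision of the plan; it does not show that the design or the planned analysis is inadequate.

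**What to change.** In the sample-size section:

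1. Reconcile the 40% and the about-half figure for PCE, saying which is expected in this study and which is carried over from the earlier one.
2. Name the test behind the detectable ORs, including any continuity correction.
3. Give detectable ORs for PCE ever/never at both 40% and 50%, with case and control counts from one scenario, for example 25, 32 and 14 cases with 710 controls as in the last table of the working.
4. Note that births exposed only to TCE leave the PCE contrast, which lowers power by an amount that cannot be computed until water modeling is done, and that trimester-specific prevalence may be below ever-exposure.

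The cost is one recalculation and the rewording of one section. No participants are added and the design does not change; the stated detectable ORs become somewhat less favourable.
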